3.1 Primary endpoint(s)

The primary objective is to demonstrate that ligelizumab doses are superior to placebo in responder rate at a level of 600 mg peanut protein (1044 mg cumulative tolerated dose) after 12 weeks of treatment.

The responder rate at 600 mg dose of peanut protein in placebo and ligelizumab groups have been assumed approximately 20% and at least 80%, respectively, for participants with evaluable DBPCFC at Week 12. These assumptions are considered highly clinically relevant based on the PALISADE trial conducted in similar populations ([Vickery et al 2018](#)). In the PALISADE trial, the responder rate at 600 mg single challenge dose of peanut protein in placebo and AR101 were 4.3% (95% CI: 1.9%, 9.7%) and 84.5% (95% CI: 79.9%, 88.1%), respectively. Approximately 15% of participants were assumed to discontinue treatment before week 12 and will be considered non-responders in power calculations. Therefore, the responder rate at 600 mg single dose of peanut protein in placebo and ligelizumab were assumed 17% and 68%, respectively, for randomized participants. For the purpose of evaluating the power for the primary trial objectives, it was assumed that none of the secondary null hypotheses would be rejected and the full alpha level of 0.025 (one-sided) would be equally split across the primary

hypotheses for each dose (i.e., 0.0125 one-sided for each testing). Under the outlined assumptions, a two group Fisher's exact test with a 0.0125 one-sided significance level will have above 99% power to detect the difference of responder rate between each ligelizumab group and placebo, when the sample size is 108 participants on each ligelizumab dose and 54 participants on placebo. Due to halt of recruitment, the sample size is expected to be around 211 (around 46 participants on each ligelizumab dose and 23 participants on placebo). This reduced sample size provides 96% power to detect the difference of responder rate between each ligelizumab group and placebo at a 0.0125 one-sided significance level. These power calculations are an approximation of the power achieved with the logistic regression approach. The table below shows the sensitivity of the power to deviations from the assumptions.

Table 3-1 Sensitivity of the power for each dose for the primary variable

RR in each QGE031 group with evaluable DBPCFC at Week 12	RR in placebo group with evaluable DBPCFC at Week 12	Drop-out rate	RR in each QGE031 group	RR in placebo group	Sample size in each QGE031 group	Sample size in placebo	Power
80%	20%	15%	68%	17%	108	54	>99.9%
80%	20%	15%	68%	17%	46	23	96%
70%	20%	15%	59.5%	17%	108	54	99.8%
70%	20%	15%	59.5%	17%	46	23	86%

RR = responder rate. Approximately 15% of participants were assumed to discontinue treatment before week 12 and be considered as non-responders in power calculations. Power results were calculated with PASS version 11.

3.2 Secondary endpoint(s)

If statistical significance is achieved in the primary test, the tests for the key secondary variables included in the testing strategy will be performed. The local significance level for each key secondary null hypothesis will be determined based on the closed testing procedure shown in [Figure 2-1](#).

Assuming a treatment discontinuation rate of 15% before week 12 and responder rates in each treatment group as shown in the table below, the local power (unconditional) of each hypothesis was estimated using 10,000 simulations with package gMCP in R 3.6.1. The assumption for maximum severity of symptoms is based on the PALISADE trial conducted in similar populations ([Vickery et al 2018](#)). The hypothesized response to 4 weeks of ligelizumab is supported by results reported in [Savage et al 2012](#) [REDACTED]. According to [Savage et al 2012](#), omalizumab increased the median tolerated threshold dose of peanut protein from 80 mg at baseline to 6500 mg at Week 5 approximately. The underlying distribution of difference in responder rate between ligelizumab and placebo is assumed to be multivariate normal in power simulations. To be conservative, correlation between endpoints was ignored for power simulation. The originally proposed sample size of 486 ensured sufficient power for primary and key secondary endpoints.

Table 3-2 Power of each dose for the analyses of primary and key secondary variables in the base case scenario

Variable	Assumptions of treatment effect	Local power (unconditional)				
		QGE031 240 mg	QGE031 120 mg	Pbo	QGE031 240 mg	QGE031 120 mg
RR of tolerating 600 mg peanut protein	RR* (RR in rand)	80% (68%)	80% (68%)	20% (17%)	>99.9%	>99.9%
RR of tolerating 1000 mg peanut protein	RR* (RR in rand)	70% (59.5%)	70% (59.5%)	20% (17%)	>99.9%	>99.9%
RR of tolerating 3000 mg peanut protein	RR* (RR in rand)	60% (51%)	60% (51%)	15% (12.75%)	>99.9%	>99.9%
Maximum severity of symptoms at any challenge dose up to and including 1000 mg#	% None	38%	38%	2%	>99.9%	>99.9%
	% Mild	32%	32%	28%		
	% Moderate	25%	25%	59%		
	% Severe	5%	5%	11%		
RR of tolerating 1000 mg peanut protein with 4 weeks of ligelizumab treatment	RR^	50%	45%	20%	98.3%	93.0%

RR=responder rate; Pbo=placebo; The proposed number of participants for comparisons between ligelizumab and placebo are 108 in each ligelizumab arm and 54 in placebo arm.

*RR is based on the anticipated proportion of responders in participants with evaluable DBPCFC at Week 12. Approximately 15% of participants are assumed to discontinue treatment before week 12 and considered non-responders for randomized population in power calculation (RR in rand). #For maximum severity of symptoms, the assumed proportion of participants in each category is based on randomized population. Power calculations were performed in R 3.6.1 with package gMCP.

^RR is based on the anticipated proportion of responders in participants with evaluable DBPCFC at Week 12. Same treatment effect is expected for randomized population in power calculation, assuming participants had taken study treatment at Week 8 and conducted DBPCFC at Week 12.

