##### **Handling of intercurrent events:**

- Discontinuation of treatment prior to Week 12: the interest lies in the responder status at Week 12 that would be observed if participants had not discontinued treatment prior to Week 12 (hypothetical strategy).
- Missing the dose of study treatment at Week 8: the interest lies in the responder status at Week 12 that would be observed if participants had not missed the dose of study treatment at Week 8 (hypothetical strategy).
- Intake of rescue medication prior to DBPCFC conducted at Week 12: ignorable (treatment policy strategy, reflected in the 'Treatment' attribute).

The same approach of handling intercurrent events will be used for events related and unrelated to public health emergency.

**Summary measure:** odds ratio comparing the proportion of responders between each ligelizumab dose group and placebo group.

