**Table 12-2 Power of each dose for the analyses of primary and key secondary variables in the base case scenario**

Variable	Assumptions of treatment effect				Local power (unconditional)	
		QGE031 240 mg	QGE031 120 mg	Pbo	QGE031 240 mg	QGE031 120 mg
RR of tolerating 600 mg peanut protein	RR* (RR in rand)	80% (68%)	80% (68%)	20% (17%)	>99.9%	>99.9%
RR of tolerating 1000 mg peanut protein	RR* (RR in rand)	70% (59.5%)	70% (59.5%)	20% (17%)	>99.9%	>99.9%
RR of tolerating 3000 mg peanut protein	RR* (RR in rand)	60% (51%)	60% (51%)	15% (12.75%)	>99.9%	>99.9%
Maximum severity of symptoms at	% None	38%	38%	2%	>99.9%	>99.9%
	% Mild	32%	32%	28%		
	% Moderate	25%	25%	59%		

[figure not shown]
any challenge dose up to and including 1000 mg#	% Severe	5%	5%	11%		
RR of tolerating 1000 mg peanut protein with 4 weeks of ligelizumab treatment	RR ^	50%	45%	20%	98.3%	93.0%

[figure not shown]
RR=responder rate; Pbo=placebo; The proposed number of participants for comparisons between ligelizumab and placebo are 108 in each ligelizumab arm and 54 in placebo arm.

\*RR is based on the anticipated proportion of responders in participants with evaluable DBPCFC at Week 12. Approximately 15% of participants are assumed to discontinue treatment before week 12 and considered non-responders for randomized population in power calculation (RR in rand).#For maximum severity of symptoms, the assumed proportion of participants in each category is based on randomized population.

Power calculations were performed in R 3.6.1 with package gMCP.

[figure not shown]
^RR is based on the anticipated proportion of responders in participants with evaluable DBPCFC at Week 12. Same treatment effect is expected for randomized population in power calculation, assuming participants had taken study treatment at Week 8 and conducted DBPCFC at Week 12.

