1.2.1 Primary estimand(s)

The primary estimand quantifies the effects of ligelizumab 120mg and 240mg SCq4w as compared to placebo on the proportion of responders at Week 12 regardless of intake of rescue medication prior to Week 12.

The primary estimand is described by the following attributes:

- **Population:** participants who have been diagnosed with IgE-mediated peanut allergy and met study inclusion/exclusion criteria.
- **Variable:** Responder status defined as tolerating a single dose of ≥ 600 mg (1044 mg cumulative tolerated dose*) of peanut protein without dose-limiting symptoms **during the DBPCFC conducted at Week 12.
- **Treatment:** the randomized treatment[^] (ligelizumab 120mg SCq4w, ligelizumab 240mg SCq4w, and placebo) plus rescue medication (e.g., epinephrine, SABA, anti-histamines), if needed.
- **Handling of intercurrent events:**
 - Discontinuation of treatment or missing more than one dose prior to Week 12: participants who discontinue treatment or miss more than one dose prior to Week 12 will not undergo any DBPCFC. They will be considered non-responders (*composite variable strategy*).
 - Intake of rescue medication prior to DBPCFC conducted at Week 12: ignorable (*treatment policy strategy*, reflected in the Treatment attribute)
Epinephrine, SABA, anti-histamines and saline bolus are typically used as rescue medication to treat allergic reactions. Participants who experience allergic reactions due to accidental exposure or other reasons may need to take rescue medications prior to Week 12. However, participants must be in good health before proceeding with the food challenge and meet the washout requirement of permitted medications as described in Protocol Table 6-2. Therefore, to reflect clinical practice, all observed values after this intercurrent event will be used in the statistical analyses whenever the treatment effect is estimated.

- **Summary measure:** odds ratio comparing the proportion of responders between each ligelizumab dose group and placebo group
- **The cumulative tolerated dose is the sum of the tolerated doses, not including the reactive dose (Casale et al 2019)*
- ***Dose-limiting symptoms indicate a true allergic reaction occurring during administration of a single dose of peanut protein at the DBPCFC that should preclude the administration of any further doses in the view of the investigator. Symptoms that require administration of any rescue medication are considered dose-limiting symptoms.*

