1.2.2 Secondary estimand(s)

The four key secondary endpoints defined in the protocol are considered for estimands as below.

1.2.2.1 Secondary estimand 1 : Proportion of responders who can tolerate a single dose of ≥ 1000 mg of peanut protein at Week 12

The secondary estimand 1 is the same as the primary estimand except that “a single dose of ≥ 600 mg (1044 mg cumulative tolerated dose)” is replaced by “a single dose of ≥ 1000 mg (2044 mg cumulative tolerated dose)”.

1.2.2.2 Secondary estimand 2: Proportion of responders who can tolerate a single dose of 3000 mg of peanut protein at Week 12

The secondary estimand 2 is the same as the primary estimand except that “a single dose of ≥ 600 mg (1044 mg cumulative tolerated dose)” is replaced by “a single dose of ≥ 3000 mg (5044 mg cumulative tolerated dose)”.

1.2.2.3 Secondary estimand 3: Maximum severity of symptoms up to and including 1000 mg of peanut protein

This secondary estimand 3 is described by the following attributes:

- **Population:** same as for the primary estimand.
- **Variable:** maximum severity of symptoms occurring at any challenge dose of peanut protein up to and including 1000 mg during the DBPCFC conducted at Week 12. According to CoFAR grading scale of dose-limiting symptoms, symptom severity will be categorized as Mild, Moderate and Severe. Symptom severity for participants who completed DBPCFC without any symptoms will be categorized as “None”.
- **Treatment:** same as for the primary estimand.
- **Handling of intercurrent events:**
 - Discontinuation of treatment or missing more than one dose prior to Week 12: Missing data at Week 12 will be replaced by the maximum severity of symptoms at screening (*composite variable strategy*).

- Intake of rescue medication prior to DBPCFC conducted at Week 12: ignorable (*treatment policy strategy*, reflected in the “Treatment” attribute).
- **Summary measure:** odds ratio comparing the odds of developing less severe symptoms between each ligelizumab dose group and placebo group.

1.2.2.4 Secondary estimand 4: Proportion of responders who can tolerate a single dose of 1000 mg of peanut protein at Week 12 with 8 weeks of placebo followed by 4 weeks of ligelizumab

The secondary estimand 4 provides insight into the treatment effect after one dose of ligelizumab. This secondary estimand is the same as the primary estimand except the following attributes :

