3.2.1 Precision for adverse events

Table 3-3 Precision levels (95% CI) for sensitivity of safety incidence rate for overall population

Event rate (proportion of participants with an event)	Number of participants	95% CI
0%	486	(0%, 0.8%)
1%	486	(0.3%, 2.3%)
2%	486	(1%, 3.7%)
0%	211	(0%, 1.7%)
1%	211	(0.1%, 3.5%)
2%	211	(0.6%, 4.9%)

4 Change to protocol specified analyses

On 31 March 2023, Novartis made a strategic decision to close recruitment in study CQGE031G12301 and terminate the study early. As a result, there are several changes to the specified analyses in the protocol, namely:

- Instead of 486 participants, the sample size is 211.

- There will be no recruitment of children under age 12, and the age-groups of interest are now 12-17 and 18-55.
- For participants who have reached Screening Visit 2 Part 1 and not completed Week 52 visit at the time of halt recruitment will need to complete Screening Visit 2 Part 2 to determine eligibility. If they are eligible, they will either continue treatment and perform assessments until Week 12 Part 2 or will stop treatment at the next scheduled visit if they have already completed Week 12 Part 2. This leads to limited number of participants reaching Week 52. Hence, non-inferiority test for sustainability of treatment effect at Week 52 compared to Week 12 is removed.
- Week 52 interim analysis will not be conducted.

There are also some changes made to simplify the analyses:

- Since the number of COVID-19 related intercurrent events is expected to be minimal, references to COVID-19 related intercurrent events were removed.
- Handling of intercurrent events for the secondary estimands were changed to be consistent with the primary estimand strategy.
- The two-dimensional tipping point analysis for the primary estimand was removed.

In analysis for primary estimand and secondary estimands(1, 2 and 4), log-transformed MTD at screening DBPCFC was added as covariate in logistic regression models.

The protocol mentions the summary measure of supplementary estimand is relative risk generated with a marginal standardization method. In SAP, relative risk is changed to risk difference to facilitate clinical interpretation.

5 Appendix

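### The 4-week row of SAP Table 3-2 still assumes the protocol's superseded hypothetical strategy; with the section's 15% discontinuation counted as non-response, power at 108/54 is about 95%/86%, not 98.3%/93.0%

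*SAP*

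**What the plan says.** Protocol 2.2.4 set a hypothetical strategy for the 4-week estimand. For discontinuation, "the interest lies in the responder status at Week 12 that would be observed if participants had not discontinued treatment prior to Week 12". For a missed Week 8 dose, the target was the status "that would be observed if participants had not missed the dose of study treatment at Week 8". The 4-week row of Protocol Table 12-2 follows that strategy: its footnote applies the evaluable-participant rates to all randomised participants, "assuming participants had taken study treatment at Week 8 and conducted DBPCFC at Week 12".

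The SAP changed the strategy. Section 1.2.2.4 says of the 4-week estimand: "This secondary estimand is the same as the primary estimand except the following attributes", and the attributes then listed are Variable and Treatment only. Intercurrent-event handling is therefore inherited from SAP 1.2.1: "participants who discontinue treatment or miss more than one dose prior to Week 12 will not undergo any DBPCFC. They will be considered non-responders". SAP section 4 confirms the change: "Handling of intercurrent events for the secondary estimands were changed to be consistent with the primary estimand strategy".

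SAP 3.2 introduces its power table with "Assuming a treatment discontinuation rate of 15% before week 12 and responder rates in each treatment group as shown in the table below". For the 600, 1000 and 3000 mg responder rows, the asterisk footnote counts that 15% as non-responders and prints a second rate for the randomised population. The 4-week row prints one set of rates (50%, 45%, 20%) with power of 98.3% and 93.0%. Its caret footnote is carried over from the protocol: "Same treatment effect is expected for randomized population in power calculation, assuming participants had taken study treatment at Week 8".

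**The concern.** The row gives power for an estimand that the SAP no longer uses. The conflict shows within the table. The same placebo arm, at the same 1000 mg threshold, has a randomised-population rate of 17% in the 1000 mg row and 20% in the 4-week row. While the two endpoints had different strategies, that difference was coherent. Under one shared composite rule it is not.

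At stake is the accuracy of a stated power for two alpha-controlled key secondary hypotheses. Table 3-2 is the only place where the SAP gives power for them.

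**Working it through.** **Inputs**

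- 108 per ligelizumab arm and 54 on placebo (note to Table 3-2).
- Evaluable-participant rates of 50%, 45% and 20% (4-week row of Table 3-2).
- 15% discontinuation before Week 12 (SAP 3.2).
- One-sided familywise alpha of 0.025, split equally between doses (SAP 2.6.2).
- Normally distributed differences in responder rate, correlation ignored (SAP 3.2).

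**Method**

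For active rate p1 and placebo rate p0, the expected statistic is

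z = (p1 − p0) / √[p1(1 − p1)/108 + p0(1 − p0)/54].

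Single-test power at level a is Φ(z − z_a), with z_a = 2.2414 at 0.0125 and 1.9600 at 0.025. The upstream hypotheses have printed power above 99.9%. Once they are all rejected, the graph in SAP 2.6.2 leaves 0.0125 on each 4-week hypothesis and passes the full level across on rejection, which is Holm's procedure. With independent statistics, the power for one dose is

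A + (B − A) × A′,

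where A and B are its single-test powers at 0.0125 and 0.025, and A′ is the other dose's power at 0.0125.

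**Step 1: reproduce the printed row (50%, 45% vs 20%)**

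| Dose | SE | z | A | B |
|---|---|---|---|---|
| 240 mg | 0.0726 | 0.30/0.0726 = 4.129 | 0.9705 | 0.9850 |
| 120 mg | 0.0725 | 0.25/0.0725 = 3.449 | 0.8864 | 0.9317 |

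- 240 mg: 0.9705 + (0.9850 − 0.9705) × 0.8864 = 98.3% (printed 98.3%).
- 120 mg: 0.8864 + (0.9317 − 0.8864) × 0.9705 = 93.0% (printed 93.0%).

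The printed figures follow from the printed inputs, so this is not an arithmetic slip. Simulations of the full ten-hypothesis graph agree: 98.3%/92.8% and 98.2%/93.2%.

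**Step 2: apply the composite rule with 15% discontinuation**

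0.85 × 50% = 42.5%; 0.85 × 45% = 38.25%; 0.85 × 20% = 17%.

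| Dose | SE | z | A | B |
|---|---|---|---|---|
| 240 mg | 0.0698 | 0.255/0.0698 = 3.652 | 0.9208 | 0.9547 |
| 120 mg | 0.0693 | 0.2125/0.0693 = 3.067 | 0.7955 | 0.8659 |

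- 240 mg: 0.9208 + (0.9547 − 0.9208) × 0.7955 = 94.8%.
- 120 mg: 0.7955 + (0.8659 − 0.7955) × 0.9208 = 86.0%.

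Full-graph simulations give 94.8%/85.9% and 95.4%/86.5%. With a correlation of 2/3 between doses for the shared placebo arm, the figures are 93.4%/85.5%.

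**Step 3: sensitivity to the discontinuation rate (same formula)**

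| Discontinuation | 240 mg | 120 mg |
|---|---|---|
| 5% | 97.5% | 91.1% |
| 10% | 96.3% | 88.8% |
| 15% | 94.8% | 86.0% |
| 20% | 92.8% | 82.9% |

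Every non-zero rate lowers both figures. None of these calculations models the covariate-adjusted logistic regression.

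**The case against.** The best defence is that Table 3-2 records the original plan. It is labelled 108/54, the SAP says in the past tense that 486 ensured sufficient power, and recruitment had already closed at 211. The row's assumption is printed directly beneath it, and no decision now depends on the figure. All of that stands, and it is why the point is minor. It does not make the row right, because nothing tells the reader that the footnote describes a strategy the SAP has replaced.

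A second objection is that 15% may not suit the placebo-8-week arms. That is fair: the documents give no arm-specific rate. Nor do they give a rate for missing only the Week 8 dose, which the protocol listed as a separate intercurrent event. The inherited rule catches only discontinuation or more than one missed dose. The corrected power is therefore conditional on the section's general 15%.

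Three stronger readings are tempting, and the documents do not support them:

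- A reader might infer that the 486 design was underpowered for this endpoint. At about 95% and 86% it was not.
- A reader might infer that the SAP conceals weak secondary power at 211. Section 3 claims sufficiency at 211 for the primary endpoint only, section 3.2 ties key secondary power to 486, and only Table 3-1 gains rows at 46/23. It is visible that secondary power was not recalculated.
- A reader might infer that the severity row is stale too, because that endpoint's handling also changed. Its footnote says only that the proportions refer to the randomised population. How they were built is not shown, so no error can be shown.

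**Conclusion.** The row is wrong as written, and the issue is minor. Its inputs belong to the protocol's hypothetical strategy, while the SAP's estimand counts discontinuation before Week 12 as non-response. On the sponsor's stated method, power at 108/54 is about 95% for 240 mg and 86% for 120 mg, a fall of about 3 and 7 percentage points. This rests on 15% discontinuation in every arm, the assumed rates among evaluable participants, normal statistics with unpooled variance, and zero correlation. The sentence that 486 ensured sufficient power still holds. The planned analysis and its type I error control are unaffected.

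**What to change.** In SAP Table 3-2:

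- Replace the caret footnote with the composite assumption already used for the asterisk rows.
- Restate the 4-week row as 50% (42.5%), 45% (38.25%) and 20% (17%).
- Re-run the simulation and print the result, expected to be about 95% and 86% at 108/54.
- Add that these figures are conditional on the section's general 15% rate, since none is given for the placebo-8-week arms or for missing only the Week 8 dose.

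A sentence that key secondary power was not recalculated at 211 would help the reader but is optional.

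The cost is one simulation run, one table row and one footnote. Estimand, model, alpha, test order and conduct stay as they are.
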